### 16.3 AE Adjudication

AEs are reviewed by sponsor on a regular, ongoing basis in accordance with the sponsor's SOP. The following is reviewed for each AE:

- Need for clarification or additional information from the site
- Appropriateness of classifications for severity, causality and expectedness
- If the AE is unanticipated, determination as to whether it poses unreasonable risk of harm to study subjects if it were to reoccur; and
- Requirements for reporting to the FDA and site IRB based on the nature of the event.

Outputs of reviews are filed by sponsor, and action items are tracked to resolution. If the investigator and sponsor do not agree on the seriousness or causality of an event, the event will be reviewed by an independent adjudicator, who is a qualified medical expert. The adjudicator is blinded to treatment assignment and will have access to the following:

- AE information reported in the EDC system
- A list of potential risks associated
- Information provided by investigators, including clinical notes, laboratory results, concomitant medications, and medical/surgical history; and
- Clinical outcome measures reported in the EDC system.

The independent adjudicator may request further information if this is required to complete AE review. The adjudicator will confirm their determination of seriousness and causality of the event. The adjudicator's decision is considered as final and is recorded in the EDC system and used in all analyses.

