Serious adverse event (SAE)	
Adverse events are considered "serious" if, in the view of either the investigator or sponsor, they result in any the following outcomes:
 
 
• Death; or
 
• A life-threatening illness or injury; or
 
• Permanent impairment of a body structure or a body function; or
 

	

• Inpatient hospitalization or prolongation of existing hospitalization; or

• Medical or surgical intervention to prevent life-threatening illness or injury or permanent impairment to a body structure or a body function; or

• Fetal distress, fetal death, or a congenital anomaly/birth defect.

 
Important medical events that may not result in death, be life-threatening, or require hospitalization may be considered serious when, based upon appropriate medical judgment, they may jeopardize the patient and may require medical or surgical intervention to prevent one of the outcomes listed in this definition.
 
Planned hospitalization for a pre-existing condition, or a procedure required by the CIP/CSP, without serious deterioration in health, is not considered a serious adverse event. [ISO 14155:2020]

Sino-Nasal Outcome Test (SNOT-22)	Validated, disease-specific, symptom-scoring instrument consisting of 22 questions, each scored by patient on a 6-point scale as follows: 

• 0: No problem

• 1: Very mild problem

• 2: Mild or slight problem

• 3: Moderate problem

• 4: Severe problem

• 5: Problem as bad as it can be

 The maximum total score for all symptoms is equal to 110.
Source data	All information in original records and certified copies of original records of clinical findings, observations, or other activities in a clinical trial necessary for the reconstruction and evaluation of the trial.
Source documents	Original documents, data, and records. Printed, optical, or electronic documents containing source data.
Subject	An individual who participates in a clinical investigation

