### 16.2.2 AE causality

The relationship of each AE to the study drug (i.e., mometasone furoate), study devices (i.e., PROPEL® Contour Sinus Implant, VenSure™ Nav Balloon Device, Cube Navigation System), and procedures (i.e., frontal BSD, implant placement) will be evaluated by PIs and categorized as defined in table below.

Strength of Relationship	Definition
Definitely	Clear-cut temporal association, and no other possible cause
Probably	Clear-cut temporal association, and a potential alternative etiology are not apparent
Unlikely	Does not follow a reasonable temporal association; or causal relationship with the drug, devices or procedures involved in the research is unlikely but cannot be completely ruled out
Not-related	AE is completely independent of study product administration; and/or evidence exists that the event is definitely related to another etiology
Indeterminate	Information gathered about the AE is not sufficient to arrive at a definite conclusion about causal relationship

Any AE that is determined by a participating investigator to be related (definitely or probably related) to the study drug, study device, or procedure will be categorized as device related. All AEs will be attributed separately to each device (i.e., PROPEL Contour Sinus Implant, VenSure™ Nav Balloon Device, Cube Navigation System), each study procedure (i.e., inflation device, BSD, implant placement), and any other in-office baseline procedures, as well as those that are a mix or indistinguishable.

For device-related AE (anticipated or unexpected/unanticipated), the sponsor may request source documentation to confirm the relationship of the AE to the study devices and may review such AE with an independent otolaryngologist, as needed.

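### Protocol 16.3 lets an adjudicator reclassify events that Section 4 and 16.2.2 already make serious or device related, and the adjudicator's blind is not reconciled with judging causality

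*Protocol*

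**What the plan says.** Three parts of the protocol decide whether an event counts as serious or device related.

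- **Section 4, SAE definition.** Events are serious if, "in the view of either the investigator or sponsor, they result in any the following outcomes". One party's opinion is enough.
- **Section 16.2.2.** "Any AE that is determined by a participating investigator to be related" (definitely or probably) to the "study drug, study device, or procedure will be categorized as device related". The rule makes no exception for a sponsor who disagrees.
- **Section 16.3.** "If the investigator and sponsor do not agree on the seriousness or causality of an event, the event will be reviewed by an independent adjudicator". The adjudicator's "decision is considered as final and is recorded in the EDC system and used in all analyses".

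On blinding, 16.3 adds: "The adjudicator is blinded to treatment assignment and will have access to the following". The list that follows covers the AE data and clinical outcome measures held in EDC, a list of potential risks, and the investigator's clinical notes, laboratory results, medications and history. The adjudicator may also ask for more. No redaction is mentioned.

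SAP 9.7 tabulates AEs, SAEs, adverse device effects, UADEs and USADEs, and lists seriousness, relationship and affected side. It does not say whose classification it uses.

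**The concern.** A definition that turns on either party's view leaves no seriousness dispute to resolve: if the two disagree, the event is serious. Section 16.3 treats the same disagreement as open and hands it to a third person with the last word. An event can then satisfy the protocol's own definition of an SAE and still appear in the tables as non-serious. The same can happen to an event that an investigator has called device related.

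The blind raises a second, separate question. Each randomized subject is assigned one implant on one side, so treatment assignment means left or right. The adjudicator is asked whether the implant or its placement caused an event, while formally not being told where the implant is.

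What is at stake is the meaning of the safety counts. Under 16.2.3 the sponsor assesses expectedness for device-related events, so a causality downgrade can also take an event out of the UADE/USADE assessment. The CT-based primary endpoint is not affected.

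**Working it through.** The plan gives no figure to reproduce here. The check is to set the rules side by side.

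**Step 1: the four disagreement patterns.** Related means definitely or probably; anything else (unlikely, not related, indeterminate) is not related for this purpose.

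| Dispute | Investigator | Sponsor | Result under Section 4 or 16.2.2 | What 16.3 can do |
|---|---|---|---|---|
| Seriousness | serious | not serious | serious (Section 4) | confirm or downgrade |
| Seriousness | not serious | serious | serious (Section 4) | confirm or downgrade |
| Causality | related | not related | device related (16.2.2) | confirm or downgrade |
| Causality | not related | related | no rule that makes it related | leave or upgrade |

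The texts collide in three of the four rows, each time towards a downgrade. In the fourth there is no collision, and 16.3 is the stated route by which the event can become device related. Section 16.2.2 is not an either-party rule: it gives force to the investigator only, and only in the direction of related.

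**Step 2: is precedence stated?** Section 16.3 says the adjudicated call enters all analyses. Neither Section 4 nor 16.2.2 yields to it, and SAP 9.7 is silent. Nothing says whether the investigator's and sponsor's calls are kept beside the adjudicated one.

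**Step 3: where does side matter?**

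- *Seriousness.* The outcomes listed in Section 4 (death, hospitalization, permanent impairment and so on) do not depend on which side holds the implant. Blinding has no bearing on this half of the problem.
- *Causality.* Frontal dilation is bilateral; the implant is on one side. Protocol 9.4 and 16.2.2 ask for separate attribution to the implant, the balloon, the dilation and the implant placement. For a one-sided local event, the implanted side is a key fact in separating implant from dilation. For systemic events it tells little.
- *Effect on the tables.* Because 16.2.2 counts drug, device and procedure alike as device related, confusing implant with dilation moves an event between attribution columns and leaves the overall device-related count unchanged. That count changes only if lack of information leads the adjudicator to a category such as indeterminate.

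**Step 4: is the blind secure?** Protocol 19.3 says treating investigators and coordinators are unblinded. The adjudicator's notes and EDC data come from those sites, with no redaction specified. Section 19.3 names only the CT reviewer as blinded.

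**Step 5: size.** The documents give no expected number of disputes. If all 80 randomized subjects enter the safety population, reclassifying the only such event in one subject moves the subject-level incidence by 1/80 = 1.25 percentage points.

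**The case against.** The best defence is a two-stage reading. Section 16.2.2 records the investigator's initial call. Section 16.3, which follows closely, reviews whether classifications are appropriate and uses an independent expert as tie-break. For causality that is a fair reading, although the order is not written down. It does not rescue seriousness, because an adjudicated ruling of non-serious contradicts the definition in Section 4 itself.

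It also stands that a reclassified event does not vanish: 16.4 records all AEs regardless of seriousness or relationship, and SAP 9.7 lists them all. Early termination under 19.10 is discretionary and has no adjudicated-count threshold.

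A reader might infer three stronger things that the documents do not support:

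- *That adjudication can only lower the counts.* The fourth row of the table shows causality can be upgraded.
- *That the adjudicator rules without knowing where the implant is.* The material supplied may well show the side. What can be said is that the blinding statement and the access list do not fit together.
- *That expedited reporting waits for adjudication.* The investigator's 24-hour and written deadlines in 16.4 are not tied to it.

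Nor do the documents require that an adjudicator be allowed only to confirm or upgrade. An impartial tie-break can go either way.

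**Conclusion.** The point holds as two separate defects of wording with a real effect on the safety tables. First, the protocol defines serious and device-related events in incompatible ways once the parties disagree. In three of four patterns, an event that meets Section 4 or 16.2.2 can be counted otherwise under 16.3. Second, the adjudicator's blind is not reconciled with the material supplied or with the causality question for one-sided events attributed to the implant or its placement.

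The size is small in number of events: disputes are likely to be few among 80 subjects, which is a judgement and not a figure from the documents. It is worth correcting because each disputed event can change an SAE or device-effect count. The conclusion rests on reading treatment assignment as implant side, which the intra-patient design implies, and on there being no redaction rule or precedence rule in the two documents supplied. The sponsor's SOP, to which 16.3 refers, was not available.

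**What to change.** 1. **Reconcile 16.3 with Section 4 and 16.2.2, and add a line to SAP 9.7.** State that the SAE and device-related tables use the Section 4 and 16.2.2 classification. Tabulate the adjudicated classification alongside, and list every reclassified event with the investigator's, sponsor's and adjudicator's calls. Amend the sentence in 16.3 on use in all analyses to match.
2. **Separate the two adjudication tasks in 16.3.** Have seriousness judged with the implant side withheld, which means removing side from the material for that step. Then have causality of one-sided events judged with the implant side disclosed. Remove the statement that causality is adjudicated blind.

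The cost is a few sentences in 16.3, a line in SAP 9.7, one extra table and some preparation of case material. The adjudicator already exists, so no extra staff are needed. The downside is that SAE and device-related counts may come out slightly higher than under the adjudicated classification alone.

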### 16.4 Guidelines for AE Reporting

All AEs, regardless of seriousness or relationship to the study devices, will be recorded in the EDC system and will include event description, date of onset, investigator's assessment of severity, relationship to study devices, and date of resolution/stabilization of the event. All AEs occurring while on study must be documented appropriately regardless of relationship. All AEs will be followed through end of the study.

Any pre-existing medical condition that is present at the time of screening will not be reported as an AE. The occurrence of diagnostic or elective surgical procedures for a pre-existing condition will not be recorded as an AE, unless the condition becomes more severe or results in an AE.

Whenever possible, diagnosis or single syndrome should be reported instead of symptoms. The investigator should specify the date of onset, severity, action taken with respect to the study device(s), corrective treatment/therapy given, additional investigations performed, outcome, and his/her opinion as to whether there is a reasonable possibility that the AE was caused by the study device(s).

The investigator should take appropriate measures to follow all AEs until resolution or until progression has been stabilized, or until study exit, to ensure the safety of the subjects. If the AE continues beyond the last planned visit per protocol and/or the subject withdraws from the study, clinical investigators should follow the subjects according to standard of care.

If a subject decides to withdraw from the study, clinical investigator should follow patients with ongoing AEs till resolution according to the standard of care.

An investigator will submit to the sponsor a report of AEs occurring during this investigation as defined in the table below.

Type of Report	Submission Schedule
Device-related AE	Verbal report or initial entry into the AE CRF within 24 hours from assessment followed by written report within 10 working days
Subject Death	Verbal report within 24 hours followed by a written report within 2 working days
SAE/SADE/UADE/US ADE	Verbal report within 24 hours followed by a written report within 5 working days

The investigator will report the above to the reviewing IRB per the IRB's guidelines. The study sponsor will be responsible for reporting safety events to the Food and Drug Administration (FDA) as required per 21 CFR 812 and 21 CFR 803.

All SAEs (SAE/SADE/UADE/USADE) will be followed until satisfactory resolution; until the investigator deems the event to be chronic or the adherence to be stable or until the subject exits the study. Other supporting documentation of the event may be requested by the sponsor and should be provided as soon as possible.

All device deficiencies including malfunctions, use errors, and inadequate labeling, will be reported to appropriate regulatory bodies and Institutional Review Boards (IRBs) as applicable.

## 17 RISK/BENEFIT ASSESSMENT

A risk/benefit analysis has been performed and a summary of the results is provided below.

## 17.1 Potential Risks

Risks associated with balloon dilation of the sinuses, as well as the placement and use of the PROPEL Contour Sinus Implant in the FSO are anticipated to be similar to those experienced by subjects who undergo balloon dilation of the sinuses as well as placement of other sinus stents.

Consequently, the risks potentially associated with the use of the sinus balloons may include but are not limited to the following:

- Epistaxis
- Cerebrospinal fluid leak
- Pneumocephalus
- Damage of the orbital wall or other ocular structures
- Impaired or loss of vision
- Impaired tearing
- Periorbital cellulitis/edema
- Infection
- Facial/nasal pain
- Facial/nasal discomfort
- Headache

Accordingly, the risks potentially associated with the placement of the PROPEL Contour Sinus Implant are:

- Special care should be taken to avoid bending, twisting or damaging the implant.
- The implant is not designed to be modified by the physician.
- The implant is not intended to be compressed and loaded into the delivery system more than two times.
- The implant must be placed under endoscopic visualization.
- The implant exhibits no antimicrobial properties.
- Foreign body reaction may occur as is possible with most surgical adjuncts.
- In rare instances, the physiochemical condition associated with sinus surgery, both with and without sinus implants or packing, may present a risk of toxic shock syndrome (TSS).
- Pediatric Use: The safety and effectiveness of the implant in pediatric patients have not been established.

- Pregnancy and Nursing Females: The safety and effectiveness of the implant in pregnant or nursing females have not been established.

Risks or side effects associated with the intranasal use of intranasal mometasone furoate (study drug):

- Nasal irritation
- Hypersensitivity reaction
- Intranasal bleeding
- Localized infection (bacterial, fungal colonization or viral) in the nose or pharynx
- Nasal burning
- Nasal dryness
- Susceptibility to secondary infections due to bacteria, fungi or viruses
- Glaucoma or elevation of intraocular pressure
- Cataracts or change in lens opacities
- Headache
- Pharyngitis

General side effects associated with steroids:

- Alteration of the HPA axis including growth suppression
- Immunosuppression
- Hypersensitivity reactions
- Headache
- Epistaxis
- Coughing
- Vomiting
- Candidiasis
- Glaucoma/elevation in intraocular pressure
- Cataracts or change in lens opacities
- Arthralgia
- Myalgia

Inhaled and intranasal mometasone furoate is generally well tolerated in clinical trials and any adverse effects are mild and generally of short duration with similar in incidence to placebo. The proportion of subjects discontinuing as a result of adverse events related to treatment is very low and generally <2-5% in most trials (Davies 1997, Drouin 1996, Graft 1996, Hebert 1996, Mandl 1997, McCormack 2006, Nayak 2002, Schenkel 2003).

Intranasal glucocorticoids may occasionally cause local adverse effects, such as a mild sensation of nasal irritation, crusting, dryness and usually minor epistaxis, however these are transient and do not worsen during long-term treatment (Mygind 2006). Local mycotic infections and septal perforations with prolonged use of nasal corticosteroids are extremely rare and have not been reported for mometasone furoate (Kyrmizakis 2000, Van Cauwenberge 2005, Vogt 1979). These findings may be related to the more rapid clearance of the topical corticosteroid by the ciliated nasal epithelium. The material used to make the implant has been used extensively in the manufacture of suture materials and other implantable medical devices and is not expected to present any new risks.

There are potential risks associated with CT scans with limited and medically acceptable dose of radiation. The radiation exposure from CT scan during this study is considered small and is not likely to affect subjects or subjects' sinus condition.

## 17.2 Minimization of Anticipated Risks

Risks associated with the PROPEL Contour Sinus Implant are minimized due to:

- The use of medical grade materials that have a long history of use and have been characterized and tested to assure biocompatibility.
- Incorporation of a very low dose (370 mcg) of mometasone furoate, the average daily release of which is below currently FDA approved intranasal doses for allergic rhinitis and nasal polyps.
- Pre-clinical evaluation including bench testing, analytical testing and animal studies.
- Prior clinical testing.
- Instructions for Use that details appropriate implant preparation and placement.
- Routine subject follow-up that includes direct endoscopic visualization of the implant and sinus tissue.
- In addition, risks will be minimized by including investigators experienced in performing sinus surgery and nasal endoscopy.

## 17.3 Potential Risks to Study Subject Confidentiality

In all clinical studies, confidentiality of protected health information may be breached due to study-related activities beyond those of routine clinical care. This risk will be minimized by not

collecting personally identifying information on CRFs or other study related documentation to be provided to the study sponsor. Any subject's personal identifying information from any documentation will be redacted by the site prior to being sent to Sponsor.

#### **17.4 Potential Benefits of Study Participation**

There may be no direct benefits of study participation. However, study subjects will undergo an enhanced level of clinical scrutiny compared to routine clinical care, which may provide some indirect health benefits.

The PROPEL Contour Sinus Implant is intended for use in patients  $\geq$  18 years of age to maintain patency of the frontal and maxillary sinus ostia following sinus surgery and locally deliver steroids to the sinus mucosa. The PROPEL Contour Sinus Implant separates/dilates mucosal tissues, prevents obstruction by adhesions/scarring, and reduces edema. The implant reduces the need for post-operative intervention such as surgical adhesion lysis and/or use of oral steroids. Addition of mometasone furoate is intended to minimize post-surgical inflammation, potentially reducing the frequency of adhesion formation and enhancing the wound healing process. Subjects may benefit from these actions. Because the implant is bioabsorbable, subjects may be able to avoid use of other sinus stents that require removal, which can be uncomfortable.

#### **17.5 Risk/Benefit Conclusion**

Based upon the Risk/Benefit Analysis performed by Sponsor, the benefits associated with the sinus implant are expected to outweigh the potential risks to the subject, and the anticipated possible risks remain reasonable and acceptable.

### **18 STATISTICAL CONSIDERATIONS**

A detailed Statistical Analysis Plan (SAP) will be prepared prior to the primary analysis through Day 45. Following is a description of the study sampling plan and a summary of the intended analyses.

#### **18.1 Randomization**

The ratio of left to right sinus assignments will be 1:1. Following bilateral frontal BSD, eligible subjects will receive 1 PROPEL Contour (treatment) on 1 side, and no implant (control) on the contralateral side. Randomization will be stratified by site and will follow a blocked scheme, with blocks of varying sizes, and will be performed using the envelope method. The randomization scheme will be generated by an independent statistician.

